## 7.2 For non-CTEP protocols only: **Expected Toxicities**

### 7.2.1 Adverse Events List(s)

Reported in 7.1.1

## 7.3 For non-CTEP protocols only: **Adverse Event Characteristics**

- **CTCAE term (AE description) and grade:** The descriptions and grading scales found in the revised NCI Common Terminology Criteria for Adverse Events (CTCAE) version 4.0 will be utilized for AE reporting. All appropriate treatment areas should have access to a copy of the CTCAE version 4.0. A copy of the CTCAE version 4.0 can be downloaded from the CTEP web site [http://ctep.cancer.gov/protocolDevelopment/electronic\\_applications/ctc.htm](http://ctep.cancer.gov/protocolDevelopment/electronic_applications/ctc.htm).
- **For expedited reporting purposes only:**
  - AEs for the agent(s) that are listed above should be reported only if the adverse event varies in nature, intensity or frequency from the expected toxicity information which is provided.
  - Other AEs for the protocol that do not require expedited reporting are outlined in the next section (Expedited Adverse Event Reporting) under the sub-heading of Protocol-Specific Expedited Adverse Event Reporting Exclusions.
- **Attribution** of the AE:
  - Definite – The AE is clearly related to the study treatment.
  - Probable – The AE is likely related to the study treatment.
  - Possible – The AE may be related to the study treatment.
  - Unlikely – The AE is doubtfully related to the study treatment.
  - Unrelated – The AE is clearly NOT related to the study treatment.

## 7.4 For non-CTEP protocols only: **Expedited Adverse Event Reporting**

7.4.1 Investigators **must** report to the Overall PI any serious adverse event (SAE) that occurs after the initial dose of study treatment, during treatment, or within 30 days of the last dose of treatment on the local institutional SAE form.

7.4.2 The following text is required for DF/HCC-led multi-institutional studies only and must be deleted for studies performed solely at DF/HCC and/or DF/PCC institutions. For multi-institution studies where a DF/HCC investigator is serving as the Overall Principal Investigator, each participating institution **must** abide by the reporting requirements set by the DF/HCC. This applies to any medical event equivalent to an unexpected grade 2 or 3 with a possible, probable or definite attribution, unexpected grade 4 toxicities, and grade 5 (death) regardless of study phase or attribution.

### 7.4.3 DF/HCC Expedited Reporting Guidelines

Investigative sites within DF/HCC and DF/PCC will report SAEs directly to the DFCI Office for Human Research Studies (OHRS) per the DFCI IRB reporting policy.

The following text and table apply to DF/HCC-led multi-institutional studies only and must be deleted for studies performed solely at DF/HCC and/or DF/PCC institutions.

Other investigative sites will report SAEs to their respective IRB according to the local IRB's policies and procedures in reporting adverse events. A copy of the submitted institutional SAE form should be forwarded to the Overall PI within the timeframes detailed in the table below.

Attribution	DF/HCC Reportable AEs				
	Gr. 2 & 3 AE Expected	Gr. 2 & 3 AE Unexpected	Gr. 4 AE Expected	Gr. 4 AE Unexpected	Gr. 5 AE Expected or Unexpected
Unrelated Unlikely	Not required	Not required	5 calendar days #	5 calendar days	24 hours*
Possible Probable Definite	Not required	5 calendar days	5 calendar days #	5 calendar days	24 hours*
# If listed in protocol as expected and not requiring expedited reporting, event does not need to be reported.					
* For participants enrolled and actively participating in the study or for AEs occurring within 30 days of the last intervention, the AE should be reported within 24 business hours of learning of the event.					

The Overall PI will submit SAE reports from outside institutions to the DFCI OHRS according to DFCI IRB policies and procedures in reporting adverse events.

For this protocol only, the AEs/grades listed below do not require expedited reporting to the Overall PI or the DFCI IRB. However, they still must be reported through the routine reporting mechanism (i.e. case report form).

CTCAE SOC	Adverse Event	Grade	Hospitalization/ Prolongation of Hospitalization	Attribution	Comments

--	--	--	--	--	--

## 7.5 Expedited Reporting to Hospital Risk Management

Participating investigators will report to their local Risk Management office any participant safety reports or sentinel events that require reporting according to institutional policy.

## 7.6 For non-CTEP protocols only: Routine Adverse Event Reporting

All Adverse Events **must** be reported in routine study data submissions to the Overall PI on the toxicity case report forms. **AEs reported through expedited processes (e.g., reported to the IRB, FDA, etc.) must also be reported in routine study data submissions.**

## 8. PHARMACEUTICAL AND/OR IMAGING AGENT INFORMATION

A list of the adverse events and potential risks associated with the investigational or other agents administered in this study can be found in Section 7.1.

### 8.1 IND Agent #1: Atorvastatin

#### 8.1.1 Description

Atorvastatin is a member of the drug class known as statins, which are used primarily as a lipid-lowering agent and for prevention of events associated with cardiovascular disease. Like all statins, atorvastatin works by inhibiting HMG-CoA reductase, an enzyme found in liver tissue that plays a key role in production of cholesterol in the body.

Atorvastatin undergoes rapid absorption when taken orally, with an approximate time to maximum plasma concentration (Tmax) of 1–2 h. The absolute bioavailability of the drug is about 14%, but the systemic availability for HMG-CoA reductase activity is approximately 30%. Atorvastatin undergoes high intestinal clearance and first-pass metabolism, which is the main cause for the low systemic availability. Administration of atorvastatin with food produces a 25% reduction in Cmax (rate of absorption) and a 9% reduction in AUC (extent of absorption), although food does not affect the plasma LDL-C-lowering efficacy of atorvastatin. Evening dose administration is known to reduce the Cmax and AUC by 30% each. However, time of administration does not affect the plasma LDL-C-lowering efficacy of atorvastatin.

It is highly protein bound (≥98%), and studies have shown it is likely secreted into human breast milk.

Atorvastatin metabolism is primarily through cytochrome P450 3A4 hydroxylation to form active ortho- and parahydroxylated metabolites, as well as various beta-oxidation metabolites. As a substrate for the CYP3A4 isozyme, it has shown susceptibility to inhibitors and inducers of CYP3A4 to produce increased or decreased plasma concentrations, respectively. This interaction was tested in vitro with concurrent administration of erythromycin, a known CYP3A4 isozyme

inhibitor, which resulted in increased plasma concentrations of atorvastatin. It is also an inhibitor of cytochrome 3A4.

Atorvastatin is primarily eliminated via hepatic biliary excretion, with less than 2% recovered in the urine. Bile elimination follows hepatic and/or extrahepatic metabolism. There does not appear to be any entero-hepatic recirculation. Atorvastatin has an approximate elimination half-life of 14 h. Noteworthy, the HMG-CoA reductase inhibitory activity appears to have a half-life of 20–30 h, which is thought to be due to the active metabolites. Atorvastatin is also a substrate of the intestinal P-glycoprotein efflux transporter, which pumps the drug back into the intestinal lumen during drug absorption.

### **Specific populations:**

**Geriatric:** Plasma concentrations of atorvastatin in healthy elderly subjects are higher than those in young adults, and clinical data suggests a greater degree of LDL-lowering at any dose for patients in the population as compared to young adults.

**Gender:** Plasma concentrations are generally higher in women than in men, but there is no dose adjustment suggested.

**Renal impairment:** Renal disease has no influence on plasma concentrations of atorvastatin and dosing need not be adjusted in these patients.

**Hemodialysis:** Hemodialysis will not significantly alter drug levels or change clinical effect of atorvastatin.

**Hepatic impairment:** In patients with chronic alcoholic liver disease, levels of atorvastatin may be significantly increased depending upon the extent of liver disease.

### **8.1.2 Form**

Atorvastatin will be given as 40 mg capsules (or 20 mg capsules if myalgias) supplied by the MGH and BWH pharmacy or the external sites pharmacy.

### **8.1.3 Storage and Stability**

The capsules can be kept at room temperature throughout the study.

### **8.1.4 Availability**

Study staff will provide pharmacy with a fund number to purchase and blind study drug. The compounding pharmacy will blind active drug and provide a matching placebo and the clinical trials pharmacy will dispense the blinded study drug to subjects free of charge.

### **8.1.5 Preparation**

The dose will be a capsules prepared by the pharmacy.

#### 8.1.6 Administration

Atorvastatin will be taken each evening. The capsules can be swallowed. If a dose is missed (not taken by midnight of the scheduled day) then the participant will not take an extra dose the following day but will just take the regular dose.

#### 8.1.7 Ordering

The agent is commercially available and will be ordered through the MGH and BWH pharmacy or the external sites pharmacy.

#### 8.1.8 Accountability

The investigator, or a responsible party designated by the investigator, should maintain a careful record of the inventory and disposition of the agent using the NCI Drug Accountability Record Form (DARF) or another comparable drug accountability form. (See the NCI Investigator's Handbook for Procedures for Drug Accountability and Storage.)

#### 8.1.9 Destruction and Return

Unused supplies of atorvastatin will be returned by the patients at each visit and destroyed immediately. Expired capsules can be destroyed per DFCI/HCC SOP since expiration dates will not be extended.

### 9. BIOMARKER, CORRELATIVE, AND SPECIAL STUDIES

#### 9.1 Biomarker Studies

We will draw blood before chemotherapy, at 3 cycles and at the end of the study (12 months treatment). We will measure biomarkers of cardiac injury, in particular troponin, which we have shown to be a predictor of later cardiac dysfunction in women with breast cancer treated with anthracyclines, taxanes and trastuzumab and correlate them with measures of cardiac function. We have already measured these biomarkers in another population.

#### 9.2 Laboratory Correlative Studies

Include the following collection/processing details when developing this section: (a) amount and type of specimen collected; (b) number, size, and type of tubes or cryovials used for collection; and (c) processing instructions.

##### 9.2.1 Troponin – Laboratory Correlative Study #1

9.2.1.1 Collection of Specimen(s)  
 30 ml of blood will be sampled.

9.2.1.2 Handling of Specimens(s)  
 Blood will be processed within 30 minutes, frozen and stored at -80°C.

9.2.1.3 Shipping of Specimen(s)  
 At regular intervals, the specimens will be shipped to the MGH where they will be stored.

9.2.1.4 Site(s) Performing Correlative Study  
 MGH/DFCI

## 10. STUDY CALENDAR

After consent is obtained, patients will undergo a baseline visit including a questionnaire, vital sign measurements, an MRI, echocardiogram and blood sampling. A pregnancy test (urine beta-HCG) will be performed as appropriate. A second visit similar to the first one will be scheduled after 3 cycles of chemotherapy (approx 3 months). The final study visit will be at 12 months where subjects will undergo an echo, MRI and blood sampling.

An additional visit for the sub-group in the MRI mechanistic sub-study will occur at 6 months where this sub-group will undergo an additional cardiac MRI.

We will do a balanced randomization with blocks of 2 patients for each cancer site.

Baseline evaluations are to be conducted within 1 week prior to start of anthracyclines therapy. Assessments must be performed prior to administration of any study agent. Study assessments and agents should be administered within  $\pm 7$  days of the protocol-specified date, unless otherwise noted.

	Pre-Study	Study Drug	1 month	2 months	3 months	6 months	12 months	24 months
Atorvastatin/placebo		X-----X						
Informed consent	X							
Demographics	X							
Medical history	X							
Perceived Stress Scale	X				X	X	X	
Physical exam	X				X		X	
Vital signs	X		X		X		X	

Height	X							
Weight	X					X	X	
Phone call: Adverse and clinical events	X		X	X	X	X	X	X
LFTS	X		X		X			
Lipids/Blood biomarkers	X				X		X	
B-HCG	X					X	X	
Echocardiogram	X				X		X	
MRI	X					X	X	
Pill count (Monthly)								

## 11. MEASUREMENT OF EFFECT

### 11.1 Other Response Parameters

The primary outcome measure is LVEF compared between groups. Specifically, we will measure the LVEF between baseline and the endpoint of the study (12 months after randomization).

The secondary outcome measures include adverse cardiac events (heart failure requiring diuretics, admission for heart failure, or death), strain and biomarkers.

## 12. DATA REPORTING / REGULATORY REQUIREMENTS

Adverse event lists, guidelines, and instructions for AE reporting can be found in Section 7.0 (Adverse Events: List and Reporting Requirements).

### 12.1 Data Reporting

#### 12.1.1 Method

The research staff will collect, manage, and perform quality checks on the data for this study via REDCAP. Outside site research staff will be given access to REDCAP after approval from OncPro and will have privileges to ensure data capture.

#### 12.1.2 Responsibility for Data Submission

The responsibility will lie on the site staff from DF/HCC, DF/PCC, and external sites to submit data and/or data forms as needed into REDCAP

## 12.2 Data Safety Monitoring

The DF/HCC Data and Safety Monitoring Committee (DSMC) will review and monitor toxicity and accrual data from this study. The committee is composed of clinical specialists with experience in oncology and who have no direct relationship with the study. Information that raises any questions about participant safety will be addressed with the Overall PI and study team.

The DSMC will review each protocol up to four times a year or more often if required to review toxicity and accrual data. Information to be provided to the committee may include: up-to-date participant accrual; current dose level information; DLT information; all grade 2 or higher unexpected adverse events that have been reported; summary of all deaths occurring within 30 days of intervention for Phase I or II protocols; for gene therapy protocols, summary of all deaths while being treated and during active follow-up; any response information; audit results, and a summary provided by the study team. Other information (e.g. scans, laboratory values) will be provided upon request.

## 13. STATISTICAL CONSIDERATIONS

### 13.1 Study Design/Endpoints

**Randomization process:** Within the DF/HCC, randomized comparative studies are conducted in a manner such that for a blinded randomization, the individual assigning study treatment is not a member of the study team but from the office for the Office of Data Quality (ODQ). Central randomization is performed according to an algorithm provided by the statistician. This will be a permuted blocks algorithm, with block size of 4. Randomized treatment assignment will be delivered to research pharmacy at the site in an unblinded fashion, and pharmacy will dispense blinded study drug. ODQ has extensive experience working with both local and distant research pharmacies on blinded randomized placebo-controlled studies, and the system is already in place.

#### **Primary End-Point**

**Our primary endpoint will be the proportion of patients in each group that have a decrease of 10% or more in LVEF to <55% from baseline to 12 months after initiation of anthracyclines.**

**Assumptions:** We anticipate that 20% of the patients in the placebo group will reach the primary end-point. This assumption is based on significant prior literature; specifically, Limat *et al.* performed a prospective study where they enrolled patients similar to those proposed in this study (lymphoma receiving anthracycline-based chemotherapy) and performed a baseline measurement of LVEF and a measurement at 1 year. Their primary end-point was a more stringent cut-off than recommended by guidelines or being used in this study, a decrease of >15% in LVEF. They found that 20% of their population had a reduction of >15% in LVEF. Using CMR, two studies have tested the percentage of patients with a significant reduction in LVEF after anthracyclines. In a prospective observational study, Drafts and colleagues found

that 26% of patients decreased their LVEF to <50% and in a prospective randomized study, Bosch and colleagues found that up to 33% of patients decreased their LVEF to <55%. In the single small randomized study which also used 40 mg of atorvastatin with 20 subjects in each arm, there was no decrease in LVEF after anthracyclines among patients on statins. Our base case assumptions are as follows: 20% of the placebo group and 5% of the statin treatment group will meet the primary endpoint and we will be able to enroll 300 patients meeting all inclusion and exclusion criteria. From these, we anticipate a drop-out rate of approximately 10% due to a one year mortality of  $\approx$ 5% and atorvastatin related side-effects in 4% of patients. The remaining 270 patients will provide us with a 98% power to detect a 15% difference in the proportions of those achieving the primary end-point at a one-sided significance level of 0.05. Moreover, we will have a 70% power if the difference in the percentage reaching the primary end-point between groups falls as low as 10%.

***Analysis Plan:*** The study is designed as a prospective double-blind randomized study. All statistical analyses will be performed based on intent-to-treat and repeat imaging will be performed at 1 year in all patients. In particular, we will include subjects who could not complete the study protocol due to statin toxicity and patients who started anthracyclines but did not complete the entire scheduled protocol. Chi-square analysis will be used to determine whether statins decrease the primary end-point.

#### **Secondary End-Points Aim 1:**

**Aim 1a.** We will test whether cardiac risks factors (blood pressure, age, sex, glucose or cholesterol levels, prior history of cardiac disease, LVEF at baseline) or cancer specific risk factors (anthracycline dose, radiotherapy) are predictive of the effect of statins on LVEF.

***Analysis Plan:*** In patients treated with statins, we will use a logistic regression model to evaluate whether cardiac risks factors or cancer specific risk factors are predictive of the effect of statins on LVEF. Patients on statins and eligible for statins will be excluded. Therefore, cholesterol levels will be relatively homogenous and we will not pre-stratify our cohort based on cholesterol. Radiotherapy is not routinely used in the cohort and is used in <5% of cases, there we will also not pre-stratify based on the use of radiotherapy. However, we will use cholesterol values (as a continuous variable) and the use of radiotherapy (as a binary variable) to perform a post-hoc analysis. Additionally, all patients are intended to have the same dose of anthracyclines and dose adjustments are made during therapy in response primarily to toxicities. Therefore, we will additionally test the interaction between the dose of anthracyclines and the effect of statins as a post-hoc analysis.

**Aim 1b.** We will test whether statins reduce cardiac events.

***Adjudication plan:*** The occurrence of clinical adverse cardiac events will be adjudicated based on consensus opinion of a clinical adjudication committee containing three board-certified cardiologists blinded to experimental group (Drs. [name], [name] and [name]).

***Analysis Plan:*** All statistical analyses will be performed based on intent-to-treat. Fisher exact tests will be used to determine whether statins decrease the combined end-point of death or heart failure.

**Aim 1c.** We will test whether statins are safe.

**Analysis Plan:** Chi-square will be used to test for differences between the two treatment groups for categorical secondary endpoints.

**Specific Aim 2:**

**Determine the effect of statins on myocardial fibrosis.** In a sub-study of 80 patients from Aim 1 (n=40 in each arm), we will measure myocardial fibrosis by calculation of the myocardial extracellular volume (ECV) using CMR, as previously described, at baseline and 6 months to determine:

- c. Whether statins prevent the anthracycline-induced increase in myocardial fibrosis at 6 months as compared to placebo.
- d. Whether a change in fibrosis or LVEF at 6 months predicts the occurrence of AIC at 12 months.

**Statistical Analysis**

**Aim 2a. Assumptions:** In our retrospective clinical study the ECV in healthy age-matched volunteers was 0.28 and was 0.04 lower than in patients treated previously with anthracyclines (0.32, mean difference and SD:  $0.04 \pm 0.05$ ). Based on these data, with 80 patients (40 from each treatment group) we will have 94% power to detect a treatment difference with a two-sided 0.05 significance level. If the actual difference in the ECV between groups is only 0.03 with a SD of 0.05, then we will still have a 75% power to detect a difference between the groups. We are assuming a 10% drop-out for participants in Aim 1. If we assume the same dropout rate for Aim 2, then our final sample size will be 36 per group. A final sample size of 72 will have a 92% power to detect a treatment difference between the means. **Analysis Plan:** The ECV is a unit-less continuous variable. The change in ECV levels from baseline to 6 months will be compared between the statin- and placebo treated groups using a Student *t* test.

**Aim 2b. Analysis plan:** The predictive value of the change in ECV between 0 and 6 months for the occurrence of the primary end-point of Aim 1 (a reduction in LVEF of  $\geq 10\%$  to less than 55% at 12 months) will be determined using a logistic regression model.

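### The Aim 2a fibrosis comparison uses a t test on change in ECV without baseline ECV as a covariate: a valid test that gives up some power for no saving

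*Protocol*

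**What the plan says.** Protocol Section 13.1, Specific Aim 2, measures ECV by CMR at baseline and 6 months in a sub-study of 80 patients, 40 per arm. Under Aim 2a the change between those visits is "compared between the statin- and placebo treated groups using a Student" t test, and no covariate is named.

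The power statement there uses a "two-sided 0.05 significance level". The planned difference is 0.04, from a retrospective comparison in which ECV in healthy volunteers was "0.04 lower than in patients treated previously with anthracyclines". The protocol states "we will have 94% power to detect a treatment difference" with all 80 patients, and 75% if the difference is "only 0.03 with a SD of 0.05". It then carries over the drop-out from Aim 1 ("We are assuming a 10% drop-out for participants in Aim 1"), so that "our final sample size will be 36 per group", with 92% power. That last figure is for the 0.04 difference. No figure is given for 0.03 after drop-out.

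No other text adds a baseline adjustment. The SAP covers only the primary endpoint and the Aim 1 secondary endpoints. The optional covariates mentioned later in Protocol Section 13.1 belong to Aims 3b and 3c.

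**The concern.** A change score fixes the coefficient on baseline at 1. ANCOVA estimates that coefficient from the data. Unless the true slope is 1, the change score carries baseline-related noise that could be removed. It also over-corrects when the arms differ by chance at baseline, which is quite possible with 36 to 40 patients per arm.

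What is at stake is precision in the trial's only randomised test of whether statins limit fibrosis, a secondary objective (Protocol Section 1.3). The primary endpoint is not touched. The loss matters most if the effect is nearer 0.03 than 0.04, because power is lower there and drop-out lowers it further.

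**Working it through.** **Inputs from Protocol Section 13.1, Aim 2a.** Two-sided alpha 0.05; difference 0.04 (planned) or 0.03 (fallback); SD 0.05; 40 per arm enrolled; 36 per arm after 10% drop-out (80 × 0.9 = 72).

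**Input not in the documents.** The correlation r between baseline and 6-month ECV. Assumed range: 0.3 to 0.9.

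**Step 1: reproduce the stated powers.** Two-sample t test, noncentral t with noncentrality d / (SD × √(2/n)) and 2n − 2 degrees of freedom.

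| n per arm | d | Noncentrality | Power | Stated |
|---|---|---|---|---|
| 40 | 0.04 | 0.04/0.01118 = 3.58 | 94.2% | 94% |
| 40 | 0.03 | 0.03/0.01118 = 2.68 | 75.5% | 75% |
| 36 | 0.04 | 0.04/0.01179 = 3.39 | 91.7% | 92% |
| 36 | 0.03 | 0.03/0.01179 = 2.55 | 70.9% | not stated |

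The stated figures are sound.

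**Step 2: compare the variances.** With the same variance σ² at both visits:

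- change score: 2σ²(1 − r)
- ANCOVA residual: σ²(1 − r²)
- ratio, ANCOVA to change score: (1 + r)/2, which is below 1 for every r below 1.

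**Step 3: power at 36 per arm, taking 0.05 as the SD of change.** The ANCOVA SD is 0.05 × √((1 + r)/2), with 69 degrees of freedom. The t test on change has 91.7% power at 0.04 and 70.9% at 0.03, whatever r is. The last column is 72 / ((1 + r)/2), the number of patients the t test would need for the same precision.

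| r | ANCOVA SD | ANCOVA power, d = 0.04 | ANCOVA power, d = 0.03 | Equivalent patients |
|---|---|---|---|---|
| 0.3 | 0.0403 | 98.6% | 87.6% | 111 |
| 0.5 | 0.0433 | 97.2% | 82.6% | 96 |
| 0.7 | 0.0461 | 95.3% | 77.7% | 85 |
| 0.9 | 0.0487 | 93.0% | 73.1% | 76 |

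**Step 4: when is the drop-out loss recovered?** ANCOVA with 36 per arm must match the t test with 40 per arm, so (1 + r)/2 ≤ 36/40 = 0.9, which gives r ≤ 0.8. At r = 0.8 and d = 0.03, ANCOVA power is 75.4%, against 75.5% for the t test before drop-out. At r = 0.9 it is 73.1%, so the loss is not fully recovered.

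**Step 5: the other reading of the SD.** The 0.05 comes from a cross-sectional comparison, so it may be a single-visit SD. The SD of change is then 0.05 × √(2(1 − r)) and the ANCOVA SD is 0.05 × √(1 − r²). At 36 per arm:

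| r | d = 0.04: t test vs ANCOVA | d = 0.03: t test vs ANCOVA |
|---|---|---|
| 0.3 | 80.8% vs 93.9% | 56.4% vs 74.9% |
| 0.5 | 91.7% vs 97.2% | 70.9% vs 82.6% |
| 0.7 | 99.1% vs 99.7% | 90.0% vs 94.0% |

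The power levels move a good deal, but the ordering does not.

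**Step 6: chance imbalance, as an illustration.** With a single-visit SD of 0.05, a one-standard-error baseline difference at 36 per arm is 0.05 × √(2/36) = 0.012. At r = 0.5 the change score passes on (1 − 0.5) × 0.012 = 0.006 of it. That is 15% of 0.04 or 20% of 0.03.

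**The case against.** The strongest reply is that nothing here is wrong. Under randomisation the t test on change is unbiased and holds its type I error. Chance imbalance at baseline affects precision and the estimate conditional on that imbalance, not validity. The endpoint is mechanistic and secondary, and at the planned effect power already exceeds 90% after drop-out. All of that stands, and it limits the point to efficiency.

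Four stronger readings are tempting, and the documents do not support them:

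- **That the plan ignores baseline ECV.** It does not: the change score subtracts each patient's baseline. What is missing is baseline as a covariate.
- **That the sub-study is planned at 71–75% power.** Those figures belong to the 0.03 fallback. The planned difference is 0.04, with a stated 92% after drop-out, and there the gain is only about 1 to 7 points.
- **That ANCOVA is sure to make good the drop-out loss.** That needs r below about 0.8, and no document gives r.
- **That the size of the gain is known.** Holding the SD of change at 0.05 implies a single-visit SD of 0.05/√(2 × 0.7) = 0.042 at r = 0.3, but 0.05/√(2 × 0.3) = 0.065 at r = 0.7. The protocol does not say which kind of SD its 0.05 is.

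What the reply does not remove is that ANCOVA uses data already being collected and is at least as powerful under both readings of the SD throughout the ranges examined.

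**Conclusion.** The point holds as a free improvement in efficiency. The planned test is valid and its power figures are correct.

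Taking 0.05 as the SD of change, with equal variances at both visits, 36 per arm and r between 0.9 and 0.3, leaving baseline out as a covariate costs about 1 to 7 points of power at 0.04 and about 2 to 17 points at 0.03. If 0.05 is a single-visit SD, the gap at 0.03 is about 18 points at r = 0.3, 12 at r = 0.5 and 4 at r = 0.7. The gain is largest where r is low, which on that second reading is also where the planned test is weakest.

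The direction is secure. The magnitude is not, because it rests on an r that the documents do not give and on an SD whose meaning they leave open.

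**What to change.** In Protocol Section 13.1, Aim 2a, and in the SAP if it is extended to Aim 2, name ANCOVA of 6-month ECV on treatment arm and baseline ECV as the analysis. Report the adjusted difference between arms with its 95% CI, and keep the t test on change as supportive. State the SD of change and the r assumed, so that the power statement can be checked against the analysis it supports.

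The change must be made before unblinding, because adjustment chosen afterwards would look driven by the data. It needs no extra patients, scans or data; the cost is a few lines of wording.
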